At visit 16 (the end of up-dosing) under intensive monitoring, all subjects who achieve 300 mg/day AR101 during the up-dosing phase for at least 2 weeks will undergo a post up-dosing DBPCFC up to 2044 mg (cumulative) peanut protein or placebo (see Appendix 1) to assess desensitization. At visit 22 (the end of maintenance period), all subjects who maintain 300 mg/day AR101 will undergo a post maintenance DBPCFC up to 2044 mg (cumulative) peanut protein or placebo to assess desensitization. Dosing with AR101 should continue on the days between the 2 parts of the DBPCFC. The subject's sensitivity to peanut allergen is defined as the dose at which the subject experiences allergic reactions. All symptoms and signs will be evaluated and rated based on a standardized oral food challenge scoring system (CoFAR) (see Appendix 2). Up-dosing during the DBPCFC will be stopped when the blinded assessor finds symptoms and/or signs that indicate a definite objective (Grade 1 [mild]) allergic reaction (CoFAR grading system [see Appendix 2]) has occurred based on clinically significant changes in reported symptoms, physical findings, or vital signs that the subject is experiencing to the challenge material. Vital signs will be assessed every 15 to 30 minutes. In addition, subjects will be considered to have dose-limiting reactions if they experience any mild subjective reactions requiring pharmacologic intervention and/or any moderate/severe reaction. The DBPCFC will consist of 8 doses (peanut protein or placebo), given every 15 to 30 minutes: 1, 3, 10, 30, 100, 300, 600, 1000 mg resulting in a total challenge of up to 2044 mg (cumulative) peanut protein. Both peanut and oat protein will be concealed in a food that masks the taste. The food challenges will be performed on different days (1-day placebo [oat] protein, 1-day peanut protein, with order determined at random) at least 24 hours, but not more than 7 days, apart, and not within 24 hours of a dose of study drug. Subjects will be considered to have passed the DBPCFC if they do not experience any objective Grade 1 (mild) reaction by CoFAR grading system (see Appendix 2). If the subject experiences reactions, he/she will be treated with the necessary rescue medications. In addition, subjects will be considered to have passed the DBPCFC if they do not experience any mild subjective symptoms requiring pharmacological intervention and/or moderate or severe symptoms. He/she will be observed for a minimum of 2 hours after the final administered dose and discharged only when deemed clinically stable by a study physician. Symptom severity will be adjudicated by an independent, blinded assessor who is not involved in subject study visit conduct. When dosing elicits an acute reaction characterized by the appearance of only a mild subjective symptom or symptoms, the investigator will be required to assess whether the dose was or was not tolerated. The determination of tolerability must be made on the basis of clinical judgement. The following are presented as guidelines for determining whether a dose associated with the emergence of a mild subjective

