
Page 49 of 118

symptom or symptoms was tolerated. A dose eliciting only mild subjective symptoms may be considered to be tolerated if the symptoms are:

- Isolated to a single organ system except for airway (including tongue) or respiratory system
- Resolve with no pharmaceutical intervention or with a single oral administration of an H1 antihistamine
- Do not require administration of epinephrine
- Are not worsening in intensity or distribution over time
- Resolve, or shows definite signs of resolving, in under 1 hour

On the day following DBPCFC, the site is to make telephone contact with the subject/subject's parent or guardian to inquire if any AEs (including allergic symptoms) occurred subsequent to the subject leaving the clinic, and to provide assistance in the recording of any such events.

Post-Treatment Follow-Up Period (12 Weeks)

All subjects will have a 12-week follow-up period after the end of treatment and will undergo safety, laboratory, and clinical assessments.

The duration of the 12-week follow-up period is based on the time expected for drug levels to fall below the lower limit of quantification after the last dose of dupilumab. At the end of the 12-week follow-up period, subjects who passed a 444 mg (cumulative) peanut protein DBPCFC at visit 22 (the end of the maintenance period, week 52 to 64 will be eligible to undergo a final DBPCFC (up to 2044 mg cumulative), under intensive monitoring, at visit 25 (end of study, week 64 to 76) to assess the level of peanut sensitivity after 12 weeks off peanut and dupilumab to determine whether there is evidence of persistent effects and sustained unresponsiveness.

Subjects who do not achieve 300 mg/day peanut protein at visit 16, (ideally week 28, and up to a maximum of week 40) will enter a 12 week follow-up period.

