7.2.2. Exclusion Criteria

A subject who meets any of the following criteria will be excluded from the study:

- 1. Any previous exposure to marketed dupilumab or dupilumab in a clinical trial
- 2. Member of the clinical site study team or his/her immediate family
- 3. History of other chronic disease (other than asthma, AD, or allergic rhinitis) requiring therapy (eg, heart disease, diabetes, hypertension) that, in the opinion of the principal investigator, would represent a risk to the subject's health or safety in this study or the subject's ability to comply with the study protocol
- 4. History of frequent or recent severe, life-threatening episode of anaphylaxis or anaphylactic shock as defined by more than 3 episodes of anaphylaxis within the past year and/or an episode of anaphylaxis within 60 days of screening DBPCFC
- 5. History of eosinophilic GI disease
- 6. Current participation or participation within 6 months prior to screening in any other interventional study.
- 7. Asthma at time of enrollment with any of the following:
 - FEV1 <80% of predicted, or ratio of FEV1 to forced vital capacity (FEV1/FVC)
 <75% of predicted with or without controller medications (only for age 6 or greater and able to do spirometry; 6 to 8 year old [Wang 1993], 8 to 18 years old [Third National Health and Nutrition Examination Survey or NHANES III -see Hankinson, 1999]) or
 - 2. Inhaled corticosteroids (ICS) dosing of >500 µg daily fluticasone (or equivalent ICS based on National Heart, Lung, and Blood Institute dosing chart) or
 - 3. one hospitalization in the past year for asthma or
 - 4. Emergency room visit for asthma within 6 months prior to screening.
- 8. Use of systemic corticosteroids within 2 months prior to screening.
- 9. Use of omalizumab within 6 months prior to screening.
- 10. Use of other forms of allergen immunotherapy (eg, oral, SC, patch, or sublingual) or immunomodulatory therapy (not including corticosteroids) within 3 months prior to screening.
- 11. Use of anti-histamines within 5 days prior to screening and within 5 days prior to SPTs and day 1 of DBPCFCs.
- 12. Use of any agents known or likely to interact with epinephrine (eg, beta-blockers, angiotensin converting enzyme-inhibitors, tri-cyclic antidepressants, or other drugs), within 3 weeks prior to screening.
- 13. Allergy to oat (placebo in DBPCFC).
- 14. Hypersensitivity to epinephrine and any of the excipients in the epinephrine product.

Regeneron Pharmaceuticals, Inc.

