8.7.1. Prohibited Medications and Procedures

Treatment with the following concomitant medications is prohibited during the study:

• Treatment with a live (attenuated) vaccine; below is a list of examples of such vaccines. Refer to study manual for a current, comprehensive list of prohibited vaccines

Chickenpox (Varicella)	Oral typhoid
FluMist-Influenza	Rubella
Intranasal influenza	Smallpox (Vaccinia)
Measles (Rubeola)	Yellow fever
Measles-mumps-rubella combination	Bacillus Calmette-Guerin
Measles-mumps-rubella-varicella combination	Rotavirus
Mumps	Varicella Zoster (shingles)
Oral polio (Sabin)	

NOTE: All subjects must have received all vaccinations per ACIP or local guidelines for measles, mumps, rubella, and varicella at least 3 months prior to enrollment in the study.

- Treatment with any agents known or likely to interact with epinephrine (eg, beta blockers, ACE-inhibitors, tri-cyclic antidepressants, or other drugs)
- Treatment with anti-histamines within 5 days prior to screening and within 5 days prior to SPTs and day 1 of the DBPCFCs

The following concomitant procedures are prohibited during study participation:

• Major elective surgical procedures

Regeneron Pharmaceuticals, Inc.

CONFIDENTIAL

Page 67 of 118

NOTE: If a subject requires a prohibited medication or procedure at any time during the study, the principal investigator should contact the Regeneron medical monitor (except for illness requiring prompt treatment). Based on the discussions, study treatment may be continued or temporarily or permanently discontinued.

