Future Biomedical Research sample (Optional)	Х			Х			Х			Х		Х
Optional Blood Samples for Additional Exploratory Research (eg, TruCulture, Basophil sensitivity, PBMC) ¹¹	Х						Х			Х		Х
PK/Drug Concentration and ADA Samples ⁴ :												
Functional Dupilumab PK Sample	Х	Х	Х	Х	Х		Х			Х	Х	Х
Anti-dupilumab Antibody Sample	Х			Х			Х			Х	Х	Х

Abbreviations: EOS, end of study; ET, early termination; WOCBP, women of child bearing potential

9.1.1. Footnotes for the Schedule of Events Table 3

- 1. The subject/legal guardian will administer SC study drug as scheduled on dosing days. Subject/legal guardian will complete an injection log (e-diary) to document compliance with injection of study drug. On days when both dupilumab/placebo study drug and AR101 are administered, the study drug will be administered at least 8 hours apart from the AR101 and at least 24 hours after the start of in-clinic dosing.
- 2. The subject/legal guardian will administer AR101 during the days in which no in-clinic visit is scheduled. Subject/legal guardian will complete a dosing diary to document compliance with AR101. On the day following in-clinic up-dosing, the site is to make telephone contact to inquire if any AEs occurred and report appropriately.
- 3. Starting at visit 4 (week 4), AR101 will be dispensed at the site to the subject/legal guardian for the doses that will be administered before the next clinic visit.
- 4. Assessments will be performed before the administration of study drug.
- 5. Subject will be observed for a minimum of 2 hours after the final administered dose and discharged only when deemed clinically stable by a study doctor. On the day following a food challenge, the site must make telephone contact to inquire if the subject experienced any AEs and report appropriately. Before each challenge, the subject will have a physical assessment performed by a trained physician's assistant, registered nurse, nurse practitioner, and/or physician of the study team who is blinded to the testing material. Eczema Area and Severity Index and ACQ only needed be completed once during day 1 of the food challenge.
- 6. Subjects should not take anti-histamines for at least 5 days prior to the SPT.
- 7. Site should confirm subject compliance at each clinic visit.
- 8. During DBPCFC, vital signs will be collected every 15 to 30 minutes. During maintenance phase for in-clinic office visits, the post-dose observation may be shortened to 30 minutes.

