4.3. Prior / Concomitant Medication and Procedures

Medications/Procedures will be recorded from the day of informed consent/assent until the endof-study (EOS) visit.

Medications will be coded to the ATC level 2 (therapeutic main group) and ATC level 4 (chemical/therapeutic subgroup), according to the latest available version of WHO Drug Dictionary (WHODD) at the coding CRO. Subjects will be counted once in all ATC categories linked to the medication.

Procedures will be coded to a Preferred Term (PT), High Level Term (HLT) and associated primary System Organ Class (SOC) according to the latest available version of MedDRA.

Prior medications/procedures: medications taken or procedures performed prior to administration of the first dose of dupilumab/placebo.

Concomitant medications/procedures (CMs/CPs): medications taken or procedures performed following the first dose of dupilumab/placebo through the EOS visit. This includes medications/procedures that were started before the study and are ongoing during the study. Furthermore, CM/CP will be categorized according to analysis periods (as defined in Section 3.3):

- CMs/CPs taken during the pre-dosing period
- CMs/CPs taken during the up-dosing period
- CMs/CPs taken during the maintenance period
- CMs/CPs taken during the follow-up period

4.4. **Prohibited or Rescue Medication/Procedure During Study**

Prohibited concomitant medications/procedures:

Treatment with the following concomitant medications is prohibited during the study:

- Treatment with a live (attenuated) vaccine (see protocol Section 8.7.1 for the list of vaccine)
- Treatment with any agents known or likely to interact with epinephrine (e.g., beta blockers, ACE-inhibitors, tri-cyclic antidepressants, or other drugs)
- Treatment with antihistamines within 5 days prior to screening and within 5 days prior to SPTs and day 1 of DBPCFCs

The following concomitant procedures are prohibited during study participation:

• Major elective surgical procedures

Rescue Treatment (including both medications and procedures)

The following concomitant treatments will require permanent study drug discontinuation:

- Treatment with an investigational drug (other than dupilumab)
- Treatment with immunomodulating biologic agents, including anti-IgE and anti-IL-5
- Treatment with allergen immunotherapy other than AR101

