| concommant treatment | vaccine per protocol | |
| Received an excluded | Treatment with an investigational drug (other than dupilumab) | - |
| concomitant treatment | (other than dupitumab) | |
| concommant treatment | | 1 |

| Category | Description of Protocol Deviation | Notes |
|-------------------------|--|-------|
| Received an excluded | Treatment with immunomodulating biologics agents, including | |
| concomitant treatment | anti-IgE and anti-IL-5 | |
| Received an excluded | Treatment with allergen immunotherapy other than AR101 | |
| concomitant treatment | | |
| Received an excluded | Treatment with systemic corticosteroids (up to PA1) | |
| concomitant treatment | | |
| Received an excluded | Treatment with any agents known or likely to interact with | |
| concomitant treatment | epinephrine (eg, betablockers, ACE-inhibitors, tri-cyclic | |
| | antidepressants, or other drugs) | |
| Received an excluded | Treatment with antihistamines within 5 days- prior to SPTs and | |
| concomitant treatment | Day 1 DBPCFCs (post randomization) | |
| Received an excluded | Major elective surgical procedures | |
| concomitant treatment | 5 6 1 | |
| Received an excluded | Treatment with systemic (oral, IV, IM, SC) corticosteroids for a | |
| concomitant treatment | duration of more than 5 continuous days, more than 15 days in | |
| | total, or within 2 days prior to DBPCFCs (PA2 and after) | |
| Received wrong | Subject given study drug but subject not randomized | |
| treatment or incorrect | , , , , , , , , , , , , , , , , , , , | |
| dose | | |
| Received wrong | Subject received incorrect treatment (wrong kit given, kit dispensed | |
| treatment or incorrect | without IVRS/IWRS transaction at re-supply visit, wrong order) | |
| dose | | |
| Received wrong | Subject received incorrect treatment or unacceptable IP (expired or | |
| treatment or incorrect | temperature excursion deemed unacceptable) that would impact | |
| dose | safety or efficacy | |
| Received wrong | Site level treatment unblinded (to for example Investigator, patient | |
| treatment or incorrect | or medical monitor) where patient care, decision making, data | |
| dose | analysis and reporting impacted | |
| Subject developed | | |
| withdrawal criteria but | Missing >2 consecutive doses of study drug (dupilumab or placebo) | |
| were not withdrawn | | |
| Subject developed | Missing >7 consecutive days of AR101 therapy (eg, concurrent | |

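### The 5-day antihistamine washout is tied only to day 1 of each two-day food challenge, so a peanut challenge on the second day can follow recent antihistamine use without any deviation

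*Protocol*

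**What the plan says.** Protocol 6.1 splits every DBPCFC into an oat day and a peanut day, in an order set at random. The on-study days must be "at least 24 hours, but not more than 7 days, apart, and not within 24 hours of a dose of study drug". AR101 continues on the days in between.

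The antihistamine rule appears in four places, each ending at day 1:

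- Protocol 7.2.2, exclusion 11: "within 5 days prior to SPTs and day 1 of DBPCFCs".
- Protocol 8.7.1, the on-study rule that applies at visit 16: "Treatment with anti-histamines within 5 days prior to screening and within 5 days prior to SPTs and day 1 of the DBPCFCs".
- SAP 4.4: "Treatment with antihistamines within 5 days prior to screening and within 5 days prior to SPTs and day 1 of DBPCFCs".
- SAP 10.6: the post-randomization deviation starts "Treatment with antihistamines within 5 days- prior to SPTs and" and finishes with Day 1 of the DBPCFCs. The matching eligibility line has the same limit.

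Day 1 means the first of the two challenge days. Footnote 5 to both Schedule of Events tables says that EASI and ACQ "only needed be completed once during day 1 of the food challenge". Protocol 6.1 starts the 24-week maintenance clock on day 1 of the visit 16 challenge but starts maintenance safety analysis after its second day.

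Protocol 8.2 lists oral antihistamines among the treatments of allergic reactions that do not lead to study drug discontinuation. Protocol 8.7.2 permits whatever 8.7.1 does not prohibit. One of the protocol 6.1 conditions for calling a challenge dose with mild subjective symptoms tolerated is "Resolve with no pharmaceutical intervention or with a single oral administration of an H1 antihistamine".

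**The concern.** The washout exists because the sponsor regards recent antihistamine use as interfering with the challenge. The day that needs this protection is the peanut day, since passing 2044 mg of peanut protein is the primary endpoint. When oat comes first, the rule protects the oat day and leaves open the interval just before peanut.

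The pass rule is sensitive to this. One objective Grade 1 sign fails the challenge, and the mild skin signs in Appendix 2 include a few hives, lip swelling, flushing and itching. An antihistamine that suppressed such a sign could turn a fail into a pass or raise the tolerated dose, which is the first secondary endpoint.

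Use in the gap is plausible. AR101 dosing continues, oral antihistamines are an accepted treatment for reactions, and subjects with allergic rhinitis or atopic dermatitis may be enrolled. A child who stopped a routine antihistamine for day 1 could resume it before day 2 and still comply with the protocol.

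**Working it through.** **1. How much of the 5 days before peanut is covered when peanut is second.** With a gap of g days, the day 1 rule covers 5 − g of those days (none once g reaches 5).

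| Gap (days) | Covered | Not covered |
|---|---|---|
| 1 | 4 | 1 (the most recent) |
| 2 | 3 | 2 |
| 3 | 2 | 3 |
| 4 | 1 | 4 |
| 5 to 7 | 0 | 5 |

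**2. Does anything else close the gap?**

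- The skin prick test footnote asks for 5 antihistamine-free days before that test. It helps only if the test is done on the second day, which is not specified.
- Protocol 8.2 limits systemic corticosteroids before DBPCFCs without a day 1 restriction, and the screening washout is counted from the peanut day. Both show wording that reaches the peanut challenge; the antihistamine rule lacks it.
- SAP 5.6.1 names only treatment discontinuation as an intercurrent event. Its one sensitivity analysis uses subjects with available challenge data, and its supportive analyses use the FAS and per-protocol set. None looks at antihistamines.

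**3. The plan's own power.** Inputs from protocol 11.2: 104 and 52 subjects, 65% and 40% passing, Fisher exact test, two-sided 5%. Exact enumeration gives 81.1%, against the stated 80%. For 122 subjects split 81 and 41 it gives 72%. No stated sample-size figure is wrong because of this point.

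**4. Illustrative size.** For each arm:

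shift in pass rate = P(peanut second) × P(antihistamine between days) × P(challenged and would fail) × P(masked)

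Assumptions, none from the documents: order 1:1; use 20% on placebo and 10% on dupilumab; half of exposed failures masked.

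- All subjects challenged: placebo 0.5 × 0.20 × 0.60 × 0.5 = 3.0 points; dupilumab 0.5 × 0.10 × 0.35 × 0.5 = 0.9 points. The difference shrinks by 2.1 points, to 22.9.
- Non-responders who were never challenged cannot be masked. Protocol section 1 says up to 20% cannot complete up-dosing. Taking 20% in each arm (an assumption), placebo is 0.5 × 0.20 × 0.40 × 0.5 = 2.0 points and dupilumab 0.5 × 0.10 × 0.15 × 0.5 = 0.4 points. The difference shrinks by 1.6 points. Subjects with peanut second number about 0.5 × 0.8 × 122 = 49, not 61.

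**5. Range.** Let m be use × masking among would-be failures with peanut second. These rows treat every non-responder as challenged, so they lean high.

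| m, dupilumab / placebo | Difference (points) | Power, 156 | Power, 122 |
|---|---|---|---|
| 0 / 0 | 25.0 | 81% | 72% |
| 5% / 5% | 24.4 | 79% | 70% |
| 10% / 10% | 23.8 | 77% | 69% |
| 5% / 10% | 22.9 | 73% | 65% |
| 10% / 20% | 20.8 | 65% | 57% |
| 0 / 20% | 19.0 | 56% | 49% |

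**6. Direction.** Swapping the use rates in the all-challenged case gives dupilumab 0.5 × 0.20 × 0.35 × 0.5 = 1.75 points and placebo 0.5 × 0.10 × 0.60 × 0.5 = 1.5 points, a widening of 0.25 points. The sign therefore depends on which arm uses more.

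**The case against.** The strongest reply is that the open interval is small and seldom used. The oat day should rarely prompt an antihistamine: oat allergy is an exclusion, and anyone with symptoms to placebo at screening is not enrolled. Subjects reach the visit 16 challenge only after at least 2 weeks at 300 mg/day. With a 24-hour gap, four of the five days are already covered. These points stand. They leave reactions to AR101 and unrelated use in a gap of 1 to 7 days, at a rate that the documents do not give.

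It can also be said that the SAP has safeguards. Section 4.4 calls for blinded adjudication of rescue treatments by type, indication, timing, frequency and potential impact, and section 10.6 is a preliminary list. Both are true, but neither says how an antihistamine between the two days would be handled or whether it would affect any analysis. The gap could still be closed before lock; as written it is open.

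A reader might infer that screening is equally exposed and the baseline tolerated dose distorted. The documents give little support for this. No AR101 is given at screening, a fully masked peanut reaction keeps the subject out, and an inflated baseline arises before randomization, so it cannot differ systematically by arm.

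**Conclusion.** The wording gap is certain: it is repeated in both documents and no other rule closes it. Following the plan as written can place the deciding peanut challenge inside the protocol's own exclusion interval, with no deviation recorded and no analysis to reveal it.

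The consequence is a possibility, not a measured bias. A reader might infer that about half of the primary results are compromised, or that the trial is biased toward placebo. The documents support neither. Half is the share with peanut second if the order is 1:1, not the share exposed to an antihistamine. The direction assumes more use on placebo. Under the stated assumptions the loss is about 1.6 to 2.1 points of a 25-point difference. The upper figure corresponds to power falling from 81% to 73% with 156 subjects, or from 72% to 65% with 122. The correction is cheap and protects the primary endpoint, so it is worth making.

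**What to change.** **Wording.** Reconcile protocol 8.7.1 first, then 7.2.2 exclusion 11 and SAP 4.4, with the random order and the 24-hour to 7-day gap, so that the protocol's own interval also reaches the peanut day. Post-screening order is blinded, so the text has to refer to both challenge days. Treatment of reactions stays as it is. The clinical interval, and whether any challenge day is moved, are for the sponsor to decide.

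**Deviation list.** In SAP 10.6, flag antihistamine use within the protocol's interval before the peanut day. Use before an oat day does not bear on the endpoint and need not be flagged. SAP 3.2 requires per-protocol decisions to be made blinded, so fix the rule before lock and apply it mechanically once challenge order is available. It needs only medication dates and challenge dates, which are already collected, and not the treatment allocation.

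**Analysis.** Add to SAP 5.6.1 a sensitivity analysis of the primary endpoint on the full mFAS that counts a pass preceded by such use as a non-response. The primary analysis assumes that no such pass was masked and this one assumes that all were, so together they bracket the effect. Do not drop these subjects: antihistamine use is post-randomization and may differ by arm, so exclusion would add selection bias.

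**Cost.** Some additional deviations logged and one extra analysis, with no new data collection.
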